Participants will be instructed not to drive an automobile or engage in any other potentially dangerous activity for the remainder of the day. The study staff will also orient the identified support person to whom the participant is being released to be available to provide emotional support, if necessary, but also to provide space if the participant would rather be alone. Each participant will be given one of the study clinician's direct pager/cellphone number to call if he/she needs support prior to their next CBT session. Within a couple of days following the drug session, participants will conduct their next weekly session of CBT, where the study clinician will inquire about any persisting or adverse effects of the psilocybin.

PARTICIPANTS:

Participants will be adults (ages 21-60) who meet current criteria for major depressive disorder.

STUDY INCLUSION AND EXCLUSION CRITERIA:

All participants must meet the following inclusion criteria to be eligible for the study:

- Ages 21-60,
- Able to swallow capsules,
- Patients with a current major depressive episode or a history of major depressive episodes based on the DSM-5 criteria (American Psychiatric Association, 2013),
- Active current depressive symptoms (i.e., scores >16 on the Hamilton-Depression Rating Scale covering the prior 2 weeks; Hamilton, 1986),
- Have an identified support person who can pick up the individual from UCLA Semel Institute and drive individual home following psilocybin sessions,
- For women of child-bearing potential – using one form of highly effective contraception (e.g., oral contraceptive pill) and willingness to continue contraceptive use for duration of study. Must be willing to take on-site pregnancy tests.
- Agree to refrain from any psychoactive drug (including alcohol) within 24 hours of each drug session and during the drug sessions. Participants will be allowed to consume their usual amount of caffeine prior to and after the drug sessions.
- Agree to not take any PRN medications on the mornings of the drug sessions
- Patient has been medically cleared for the study by a physician
- Participants must remain on anti-hypertensive medications if prescribed previously to manage hypertension

Participants will not be enrolled in the study if they meet any of the following exclusion criteria:

- A personal or family history (first or second-degree) of psychosis or bipolar disorder

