- Resting blood pressure above 140 systolic, 90 diastolic or heart rate > 90 beats per minute (averaged across four separate measurements)
- Meeting criteria for a DSM-5 cluster B personality disorder (narcissistic, histrionic, borderline, antisocial personality disorder),
- Active suicidality (i.e., HAM-D item 3 score of 3 or greater) or other psychiatric disturbance requiring acute treatment

- Current use of antidepressants or other serotonergic-affecting substances (e.g., St. John's Wort and 5-hydroxytryptophan), lithium, or efavirenz [regardless of whether the drug(s) is/are prescribed for MDD or other conditions]
- Current use of opioids (e.g., codeine, fentanyl, hydrocodone, meperidine, tramadol)
- Currently receiving cognitive behavioral therapy,
- Any of the following cardiovascular conditions: uncontrolled hypertension, coronary artery disease, congenital long QT syndrome, cardiac hypertrophy, cardiac ischemia, congestive heart failure, myocardial infarction, tachycardia, artificial heart valve, a clinically significant screening ECG abnormality, or any other significant cardiovascular condition
- QTc interval measurement of > 450 ms in males or > 460 ms in females as measured by the baseline ECG
- A history of stroke or Transient Ischemic Attack (TIA)
- Epilepsy or history of seizures
- Insulin-dependent diabetes
- Meeting criteria for a DSM-5 substance abuse or dependence within prior 6 months (including for nicotine and cannabis)
- Positive urine drug screen for illicit substances (not including cannabis)
- Use of other psychedelics or ketamine within prior 12 months
- Adverse prior reaction to a 5-HT_{2A} receptor agonist psychedelic agent
- Pregnant, trying to get pregnant, or nursing

SCREENING AND TESTING PROCEDURES:

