agents, lithium, or efavirenz (regardless of whether the drug(s) is/are prescribed for a depressive disorder or another condition). Additionally, participants will be excluded if they are taking agents that may interact with psilocybin metabolism/effects (e.g., antipsychotics, other dopamine antagonists) or agents that may increase the risk of psychotic symptoms (e.g., dopamine agonists, stimulants). The study team will not work with subjects to taper them off medications. Subjects will be excluded if they, prior to screening, have not already discontinued any medications excluded for this study.

The results of the physical screening (including the blood panels, urine toxicology, and ECG) will be reviewed by a study physician. To be eligible, participants must have a clear ECG screening (no clinically significant abnormalities and QTc measurement > 450 milliseconds in males or > 460 milliseconds in females). Participants will also be excluded if they report or are found to have any cardiovascular conditions, including uncontrolled hypertension, coronary artery disease, congenital long QT syndrome, cardiac hypertrophy, cardiac ischemia, congestive heart failure, myocardial infarction, tachycardia, artificial heart valve, a clinically significant screening ECG abnormality, or any other significant cardiovascular condition. A personal history of stroke, Transient Ischemic Attack (TIA), hepatic impairment, epilepsy, and insulin-dependent diabetes will also be exclusionary. Individuals who have any medical conditions or take medications that are exclusionary for this study will be withdrawn from the study. In addition to a negative pregnancy test, women of child-bearing potential will need to be on at a form of highly effective contraception (e.g., oral contraceptive pill) for at least one month prior to study entry and for the duration of the study.

For individuals with whom the study physician requires more clarification regarding their medical condition(s) or medications, a release of information (ROI) will be obtained to consult with the participant's primary care physician. For participants with which the study physician cannot gather a clear medical history or in which there is ambiguity around whether they meet criteria for any of the above-mentioned conditions will be excluded from the study. Participants who do not clear the medical screening will be withdrawn from the study.

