Appendix I. Case Report Form

Appendix II. Music Playlist

Appendix III. Drug Management Protocol

Appendix IV. Security Provisions for Drug Storage

Appendix V. Controlled Substances Usage Log

Appendix I. Case Report Form

DCI
Cancel

Subject ID: _____ Date: _____ Monitors: _____ Session: 1-10mg

Ideal Time	Actual Time	Activity	BP	HR	Rescue drug administered	Study Questionnaires	Persisting effects	Oriented X4	Important Event Reporting
8:00		U-tox & pregnancy screen							
8:30		Review study procedures							
9:00		Administer Psilocybin							
9:30		Time Point 1							
10:00		Time Point 2							
10:30		Time Point 3							
11:00		Time Point 4							
11:30		Time Point 5							
12:00		Time Point 6							
12:30		Time Point 7							
1:00		Time Point 8							
1:30		Time Point 9							
2:00		Study Questionnaires							
3:00		Discharge							

*Bolded activities require BP and HR measurement

BASELINE QUESTIONS	
Last food: _____	Unusual physical symptom or stress: Y / N
Last caffeine: _____ or Not Regular User	(Must be N)
Normal? Y / N	Anti-hypertensive medication taken: Y / N / NA
Last nicotine: _____ or Not Regular User	(Must be taken as prescribed within past 24 hours, if prescribed)
Normal? Y / N	Pregnancy Test: Positive / Negative
Last alcohol: _____ or Not Regular User	(Must be negative)
(Must be > 1 day)	Drug Test: Positive / Negative
Last cannabis: _____ or Not Regular User	(Must be negative)
(Must be > 30 days)	Identified support person for pick up:
Last PRN: _____ or Not in Last Month	
(Must be > 6 hours)	

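### Eligibility and dosing-day rules conflict on cannabis and diagnosis, and are inconsistently worded on QTc and hepatic impairment

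*Combined protocol and SAP*

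**What the plan says.** The rules are spread over the combined protocol and SAP.

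- **Cannabis at entry.** The exclusion list under Study Inclusion and Exclusion Criteria has "Positive urine drug screen for illicit substances (not including cannabis". The list under Adequacy of Protection Against Risks and the withdrawal list under Participant Monitoring and Removal from the Study make the same exemption. The withdrawal list also governs findings made during the study. The inclusion criterion on abstinence reads "Agree to refrain from any psychoactive drug (including alcohol) within 24 hours of each drug session and during the drug sessions".
- **Cannabis on dosing day.** The General Investigational Plan requires negative toxicology before dosing and states no cannabis exception. The Appendix I case report form (shown for the 10 mg session) requires a negative drug test and, for last cannabis use, "Must be > 30 days".
- **Diagnosis.** The Participants section says "Participants will be adults (ages 21-60) who meet current criteria for major depressive disorder". The inclusion list, directly below, accepts "Patients with a current major depressive episode or a history of major depressive episodes based on the DSM-5 criteria", together with a HAM-D score above 16.
- **QTc.** Screening and Testing Procedures says that an eligible participant must have a clear ECG, and explains this in brackets as "no clinically significant abnormalities and QTc measurement > 450 milliseconds in males or > 460 milliseconds in females". All three lists exclude "QTc interval measurement of > 450 ms in males or > 460 ms in females as measured by the baseline ECG".
- **Hepatic impairment.** Screening and Testing Procedures says "A personal history of stroke, Transient Ischemic Attack (TIA), hepatic impairment, epilepsy, and insulin-dependent diabetes will also be exclusionary". Stroke/TIA, epilepsy and insulin-dependent diabetes from that sentence appear in all three lists. Hepatic impairment appears in none.

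**The concern.** Feasibility is a primary objective. The analysis plan measures it by the percentages enrolled and retained through treatment. If the protocol's own rules admit someone and then bar that person from dosing, the loss will look like poor feasibility of the treatment when part of it comes from the wording. Whether that person counts as lost or retained also depends on the section applied.

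The diagnosis line decides which population the HAM-D change describes. The QTc and hepatic items matter differently: they are safety exclusions, and staff working from one page should reach the same answer as staff working from another.

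**Working it through.** The documents give no figure to reproduce, so the check takes one hypothetical person per topic and applies each rule as written.

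| Person | Passes under | Fails under |
|---|---|---|
| Non-dependent cannabis user, last use 10 days before dosing | 24-hour inclusion criterion; all three lists (cannabis exempt) | Appendix I (more than 30 days); also the negative-toxicology rule if the test still reads positive for cannabis |
| Past depressive episode only, HAM-D of 17 | Inclusion list | Participants section (current disorder) |
| Man with QTc of 455 ms | Literal bracket in Screening and Testing Procedures | All three lists |
| Man with QTc of 420 ms | All three lists | Literal bracket in Screening and Testing Procedures |
| Person with hepatic impairment | All three lists (not named) | Screening and Testing Procedures |

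**Can the cannabis case arise in practice?** The first dose follows the third CBT session, and CBT is weekly, so session 3 falls about 2 × 7 = 14 days after session 1. The protocol's durations suggest a little longer: a 7-month study with monitoring for up to 6 months after the first dose leaves 7 − 6 = about 1 month. On either count, a person who stops cannabis when CBT starts is not assured of more than 30 days by the first dose.

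**What happens to that person?**

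- The General Investigational Plan removes from the study anyone positive for illicit drugs. The section on drug and medication restrictions says the same.
- The text after the withdrawal list keeps people withdrawn on a listed criterion in CBT without psilocybin once CBT has begun. That list exempts cannabis, so the provision does not clearly reach this person.
- Whether cannabis counts as illicit on dosing day is not stated.

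**Size on the feasibility percentages.** One participant is 100/N points, where N is the denominator.

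- Among the 30 planned participants: 100/30 = 3.3 points.
- The analysis plan divides by those consented and screened, a number the documents do not give. With 60 (assumed): 100/60 = 1.7 points.
- N would equal 30 only if nobody failed screening, so for a planned sample of 30, 3.3 points is an upper bound per person on the stated metric.

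How many people would be affected is not given and cannot be derived.

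**The case against.** The strongest reply is that most of this is untidy wording around rules that work together.

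- **QTc.** If the word no governs both items in the bracket, the text agrees with the lists. The next sentence excludes long QT syndrome and significant ECG abnormalities, and a study physician reviews every ECG. A reader might infer that the rules taken together leave no ECG that qualifies. That follows only from a reading few would apply. What stands is that a safety threshold should not depend on a charitable reading.
- **Hepatic impairment.** Nothing permits it. Exclusions are cumulative, liver tests are ordered, a physician must clear each participant, and ambiguous cases are excluded. It is an omission from the lists, not an opposite statement. What stands is that the lists are incomplete, including the one used during the study.
- **Cannabis.** Anyone who meets 30 days also meets 24 hours, and a stricter rule at a later time point can be deliberate. A reader might also infer that a cannabis-positive participant is certainly removed, but the removal sentence covers illicit drugs only. Use after agreeing to the study's drug restrictions is also partly the participant's choice. What stands is that the in-study list exempts a positive screen which the dosing-day rules do not, and that nobody is told at entry about a 30-day condition.
- **Diagnosis.** The inclusion list may be the operative rule and the Participants line a summary. Both readings need a HAM-D above 16, so only people with a past episode and no current one are affected. But a severity score shows current symptoms, not a current diagnosis, so the two lines still differ.

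**Conclusion.** The point holds, with its parts at different strengths. Cannabis and diagnosis are direct conflicts in the current text: the same person gets different answers under different lines. The QTc wording is probably a slip, but as written it reverses a safety limit. Hepatic impairment is a gap in three lists whose screening text already excludes it.

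The size is unknown. A reader might take 3.3 points off retention per affected participant, or 10 points if 3 of 30 were affected (3/30). The documents do not support either as a forecast. The number affected has no basis in the text, the stated denominator is those consented and screened, and some of these participants may be kept in CBT and counted as retained. The conclusion rests on comparing the text and needs no assumption about power, alpha or effect size. It should still be fixed, because it bears on who is enrolled and dosed and on a safety threshold, and the repair is only wording.

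**What to change.** Reconcile the General Investigational Plan, Participants, Study Inclusion and Exclusion Criteria, Screening and Testing Procedures, the exclusion list under Adequacy of Protection Against Risks, Participant Monitoring and Removal from the Study, and Appendix I into one eligibility list and one dosing-day list, and have every other section refer to them. In doing so:

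1. State how the entry and dosing-day cannabis rules relate, and whether cannabis counts in the dosing-day drug test. The two time points need not share a rule, but the relation must be explicit.
2. State what happens to a participant who fails the dosing-day rule, and how that person is counted in the enrolment and retention percentages.
3. Use one diagnostic criterion throughout.
4. Word the QTc limit in the same direction everywhere.
5. Treat hepatic impairment the same way in the screening text and all three lists.

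The clinical content of each rule is for the study physicians. The cost is protocol and form wording, and possibly a few more screen failures.

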[name], MPH, MBA; Associate Professor of Psychiatry; UCLA Semel Institute. [name] is a psychiatrist who serves as the Medical Director and lead psychiatrist of UCLA's Behavior Health Access.

[name]; Professor of Psychiatry; Harbor-UCLA Medical Center and UCLA Semel Institute. [name] is a psychiatrist and renowned expert in psychedelic treatment for psychiatric disorders.

Research Facility: UCLA Semel Institute – [name].

Institutional Review Board: UCLA Office of Human Research Protection Program, [name].

Specific Aims

The primary objectives of this clinical investigation are (1) to determine the acceptability and feasibility of joining psilocybin treatment with cognitive-behavioral therapy (CBT) for patients with depression, and (2) to determine the initial effect of psilocybin as an adjunct to CBT for major depressive disorder. Psilocybin will be administered orally in two doses during a 12-session CBT treatment to eligible study participants – a 10mg dose following the third session and a 25mg dose following the sixth session.

We hypothesize that psilocybin as an adjunct to 12 sessions of CBT will

- (1) Be feasible and reviewed favorably by participants,
- (2) Lead to improvements in depressive symptoms.

Background

Psilocybin (3-[2-(dimethylamino)ethyl]-1H-indol-4-yl] dihydrogen phosphate) is a natural product produced by numerous species of *Psilocybe* mushrooms. It is a tryptamine derivative, and in humans is rapidly enzymatically broken down to produce psilocin, which acts as a serotonin agonist (Carhart-Harris et al., 2014; Nichols, 2004). Psilocybin is classified as a Schedule I pharmacological substance by the DEA.

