Cognitive behavioral therapy (CBT) is considered the gold-standard of empirically-based psychosocial treatments for depression (Cuijpers et al., 2013). Thus, CBT may serve as a useful, standardized foundation of psychosocial treatment to provide for patients with depression who are receiving psilocybin treatment. Additionally, psilocybin may help facilitate the uptake of CBT skills. Since psilocybin engenders greater cognitive flexibility and behavioral motivation (e.g., greater openness and social connectedness), it may help facilitate the uptake of CBT skills. Depressed individuals’ negative beliefs and unhelpful behaviors can become quite fixed, which can make treatment progress slow. Together, psilocybin may be a helpful catalyst for the cognitive and behavioral changes that are sought in CBT, and CBT may help to solidify cognitive and behavioral changes that are spurred by the psilocybin experience.

This study seeks to build on the current approaches to psilocybin treatment by combining CBT with the already-established psilocybin + PAT approach to (1) test whether CBT can be feasibly and acceptably added to the current psilocybin treatment modality and (2) to work towards protocolizing the psychosocial treatment that adjoins psilocybin drug therapy.

GENERAL INVESTIGATIONAL PLAN:

This study is a preliminary, proof-of-concept pilot to determine feasibility of the treatment methods and effect sizes. The study design is a single-group, fixed dose trial whereby 30 eligible participants will undergo 12 sessions of CBT during which two doses of psilocybin will be administered— a 10mg dose following the third session and a 25mg dose following the sixth session. Participants will be followed for an additional 3 months following treatment

termination. Study procedures will follow previously established safety guidelines (Johnson et al., 2008).

We hypothesize that psilocybin as an adjunct to 12 sessions of CBT will:

- (1) be feasible and reviewed favorably by participants, with minimal to no adverse effects;
- (2) Lead to reductions in negative thinking, increases in engagement with the environment, and improvements in depressive symptoms over the 7-month study period.

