PRIMARY OUTCOME MEASURES AND STATISTICAL ANALYSIS PLAN:

The study's primary assessments will be held prior to starting the CBT (i.e., baseline), within two weeks following the CBT's completion, and three months following the treatment's completion. Secondary measurements will also be collected immediately following each drug session. The study will terminate following the three-month follow-up assessment. A schematic of the study design is presented in Figure 1 below.

To determine feasibility, we will track the number of participants engaged at each phase of screening (i.e., phone screen, physical screen, and psychological screen), the number consented and enrolled, and the number who completed the 4-month treatment. Acceptability was measured by participants at the post-treatment assessment using the Client Satisfaction Questionnaire 8 (CSQ-8; Larsen et al., 1979). Participants' and clinicians' quantitative and qualitative feedback will be collected, using an internally-created questionnaire containing 5-point scales of helpfulness. Depressive symptom severity over the previous 1-2 weeks will be assessed using the 17-item Hamilton Depression Rating Scale (HAM-D; Hamilton, 1986). Psychosocial functioning over the two weeks prior to the assessment will be rated by a study assessor assessed using the 100-point Global Assessment of Functioning Scale (GAF; American Psychiatric Association, 2000).

Feasibility metrics will be tabulated by calculating percentages of participants enrolled and retained through the treatment divided by the total number of participants consented and screened. Acceptability metrics will be calculated based on the participant-rated CSQ-8. We will calculate the mean and standard deviation. We will examine within-subjects changes in depressive symptoms (HAM-D) and functioning (GAF) using repeated measures analyses of variance (ANOVA) in IBM's SPSS version 30.0. Time will be the independent fixed factor variable, based on the interval assessments of the study (baseline, post-treatment, follow-up).

Figure 1. Study Design Schematic for Eligible Participants

STUDY DRUGS:

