Interested individuals will contact a research associate, who will provide information about the study. Potential participants will be given opportunities to ask questions about the study. A brief screening will be conducted with the interested individual. If the potential participant appears eligible agrees to an initial evaluation, a first appointment will be scheduled for consenting and eligibility assessment. At this meeting, the study team will explain the study procedures and ask for written consent from the participant. The participant will then undergo the study assessment process - medical screenings, diagnostic interview, and complete initial self-report measures.

Protection Against Risk:

Training of Study Monitors in Psychedelic Assisted Therapy (PAT): [name], and [name], (licensed clinical psychologists) will be trained in PAT by [name] and [name], MPH, MBA. [name] has led and consulted on previous research trials using psilocybin and has significant experience leading PAT sessions. [name] is certified in PAT following intensive training from the Integrative Psychiatry Institute (IPI) and the Multidisciplinary Association for Psychedelic Studies (MAPS). [name] had extensive 200-hour training in Psychedelic-Assisted Psychotherapy (PAT) from the IPI between 2021-2022. As part of this training, she led multiple PAT sessions using ketamine and she has continued to provide PAT with ketamine to patients in her private practice since completing her training. [name] also completed the 100-hour MAPS PAT training program for MDMA-assisted therapy in 2022.

The trainings for this study are modeled after the trainings conducted for [name] previous psilocybin trial. The trainings will first involve structured didactics in the methods of PAT, management of difficult experiences patients may have, and crises that may arise. Following the didactics, Drs. [name] and [name] will facilitate role-plays to practice common psilocybin-induced scenarios and PAT practices. The PAT training plan for will be conducted as follows:

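### The only retention percentage specified divides by everyone consented and screened, so it counts screen failures as not retained and does not measure retention on treatment.

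*Combined protocol and SAP*

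**What the plan says.** Specific Aims lists as the first primary objective "to determine the acceptability and feasibility of joining psilocybin treatment with cognitive-behavioral therapy (CBT) for patients with depression". The section Primary Outcome Measures and Statistical Analysis Plan gives one rule for the feasibility percentages: they are obtained by "calculating percentages of participants enrolled and retained through the treatment divided by the total number of participants consented and screened". Earlier in the same section the plan undertakes to record headcounts at the phone, physical and psychological screens, and also "the number consented and enrolled, and the number who completed the 4-month treatment".

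The order of events is set out under Recruitment and Informed Consent. After a brief screen of interested people, "a first appointment will be scheduled for consenting and eligibility assessment". Written consent is sought at that meeting, and only afterwards: "The participant will then undergo the study assessment process - medical screenings, diagnostic interview, and complete initial self-report measures". Screening and Testing Procedures says that people who do not clear the medical screening are withdrawn.

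The plan states no expected number screened, no expected retention and no threshold for calling the treatment feasible.

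**The concern.** Because consent precedes the eligibility work-up, everyone who consents and then fails screening sits in the denominator. That suits a measure of recruitment yield. It does not suit retention: a person who was never eligible cannot be retained, yet is counted as not retained. The rule can be read as one percentage or as two (enrolled over screened, retained over screened). On either reading, retention carries the screened denominator, and no percentage among those enrolled or treated is specified.

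Retention on treatment is a direct measure of whether CBT and psilocybin can be joined in practice. If the rule is followed as written, the reported figure will understate retention by a factor that depends on how strict the screening was. If it is not followed, the denominator will have been chosen after the results are known.

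The numerator is also loose. Under Participant Monitoring and Removal from the Study, *retained* also describes people who continue CBT after being barred from further psilocybin sessions. Someone who missed a psilocybin session could therefore count as retained in a study of the combination.

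**Working it through.** **Inputs**

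- Enrolled, E = 30, from the General Investigational Plan: "30 eligible participants will undergo 12 sessions of CBT during which two doses of psilocybin will be administered". I assume that all 30 start CBT, so enrolled and started coincide in the illustration.
- Completed, C: no expected value in the documents. Assumed 18, 24 or 30.
- Consented and screened, S: not in the documents. Assumed 30 to 150.
- The plan gives no retention figure of its own, so there is nothing to reproduce.

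**Step 1: what the specified percentage measures**

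C/S = (E/S) × (C/E), that is, screening yield × retention among the enrolled. The two agree only when S = E, meaning no screen failures after consent.

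**Step 2: fix retention, vary the number screened**

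Take C/E = 24/30 = 80.0% (exact Clopper-Pearson 95% CI 61.4 to 92.3).

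| S (assumed) | Yield 30/S | Specified percentage 24/S |
|---|---|---|
| 30 | 100.0% | 80.0% |
| 45 | 66.7% | 53.3% |
| 60 | 50.0% | 40.0% |
| 75 | 40.0% | 32.0% |
| 100 | 30.0% | 24.0% |
| 150 | 20.0% | 16.0% |

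The same dropout gives anything from 80% to 16%. A confidence interval does not repair this: the exact interval for 24/60 is 27.6 to 53.5%, which excludes the 80% retention that produced it.

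**Step 3: fix the specified percentage, vary retention**

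Three different trials all report 40.0%:

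- 18/45, where retention is 18/30 = 60.0% (40.6 to 77.3)
- 24/60, where retention is 24/30 = 80.0% (61.4 to 92.3)
- 30/75, where retention is 30/30 = 100% (88.4 to 100)

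The percentage alone cannot separate substantial dropout from none.

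**Step 4: the ceiling**

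With no dropout, C = E and the percentage equals the yield. If 60 are screened it cannot exceed 30/60 = 50.0%.

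**Step 5: can the right rate be recovered?**

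Yes. The plan tracks both the number enrolled and the number completing the four-month treatment. From 24 and 30 the result is 80.0% (61.4 to 92.3), whatever the number screened.

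**The case against.** The strongest reply is that nothing is lost. The plan speaks of metrics and percentages in the plural, and it tracks enrolment and completion separately, so any reader given those counts can divide one by the other. Completion over the whole screening funnel is also a legitimate figure for a pilot with long exclusion lists, and enrolled over screened is plainly useful. This is a single-group pilot with no feasibility threshold, so no decision turns on the ratio. The brief screen before the consent visit will remove some ineligible people, so S may be closer to 30 than the larger values above; at S = 36, for example, 24 completers would give 24/36 = 66.7%.

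Much of this stands. A reader might infer that the trial cannot show whether the treatment is feasible. The documents do not support that, because the counts needed are tracked. A reader might also take this percentage for the primary feasibility figure, but the plan designates no such figure. What does not stand is that tracked counts make the rule harmless: they do not say in advance which ratio will be reported as retention, and the one rule given has the wrong denominator.

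A reader might extend the point to acceptability, since the plan says "Acceptability was measured by participants at the post-treatment assessment using the Client Satisfaction Questionnaire 8", and conclude that satisfaction comes only from those who stayed. The documents do not support that either. Under Participant Monitoring and Removal from the Study, the team undertakes to try to keep withdrawn participants for study assessments, with their consent. Some forms may still be missing, but the documents give no basis for sizing the effect. Collecting the questionnaire at withdrawal would add data collection and mix ratings of partial and full treatment. It is not part of this point.

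**Conclusion.** The point holds for the percentage as specified. It equals screening yield times retention, so it understates retention whenever anyone who consents fails screening. With 24 of 30 completing, 80% would be reported as 53%, 40% or 24% at 45, 60 or 100 consented and screened. These sizes rest on assumed numbers screened and completing and on all 30 enrolled starting CBT. The direction does not depend on the assumed numbers: it follows from consent preceding screening and applies for any S above 30.

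The error is in a stated rule serving the first primary objective, and it should be corrected in the plan. It is an error of definition; the data to be collected are adequate. Correcting the denominator will not supply a criterion for calling the treatment feasible, since the plan sets none.

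**What to change.** Replace the sentence with two pre-specified rates, each with an exact 95% confidence interval:

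1. Enrolment yield = enrolled / consented and screened.
2. Retention = completed the four-month treatment / enrolled participants who started CBT.

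Beside them, report the shares of those who started CBT who received the first and the second psilocybin session, so that people who stayed in CBT without psilocybin are visible. State whether *screened* includes the brief screen before consent. The funnel percentage may be kept as a further line if it is labelled as such.

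The cost is a short edit to the analysis plan. Enrolment, completion and drug administration are already to be recorded, so no visit, form or participant is added, and the downside is negligible.
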